1.2.1.2 Non-clinical safety pharmacology and toxicology

For a more detailed description of the BI 425809 profile, please refer to the current Investigator's Brochure (IB) [[c02155957](#)].

1.2.1.3 Clinical experience in humans

At the time of preparation of this clinical trial protocol, BI 425809 has been investigated in eight Phase 1 trials (7 of them already reported; one trial (1346-0016 [[c11975084](#)]) clinically completed, data on file). Two Phase 2 trials (1346-0009 [[c03559983](#)] and 1346-0023 [[c03632269](#)]) and one Phase 1 trial (1346-0015 [[c21363182](#)]) are ongoing.

More than of 245 healthy subjects have received one or more doses of BI 425809 (single doses of 0.5 mg to 150 mg and multiple doses of 5 mg to 75 mg bid (150 mg/day)), including 18 subjects aged 65 years or older (for details please refer to Investigator's Brochure, Table 6.1: 1 [[c02155957](#)]).

Altogether, BI 425809 was generally well tolerated in young and elderly healthy male and female volunteers. No deaths or serious adverse events (SAEs) and no AEs of special interest (AESI) were reported. Across all BI 425809 treatment groups, there were 3 subjects with severe, but self-limiting AEs. Overall, drug-related AEs have been seen more frequently in the subjects treated with BI 425809 (33.5% vs 26.9% on placebo). Across all BI 425809 treatment groups, 3 subjects discontinued treatment due to an AE (2x nausea and vomiting, 1x procedural headache), all subjects recovered (for details please refer to Investigator's Brochure, Table 6.3.1.1: 3 [[c02155957](#)]).

The most frequent AEs for BI 425809 were nervous system disorders (25.3%), with headache being the most common (18.0%). These AEs appear to be dose-related, with a tendency for greater frequency at higher doses and can be clinically monitored.

In addition, transient visual disturbances (at doses \geq 25 mg BI 425809 qd, mainly blurred vision) and somnolence (drowsiness) were observed. These effects are mostly mild to moderate and transient.

In general, there were no clinically relevant findings in the clinical laboratory evaluation, 12-lead ECG, vital signs. No suicidal ideation or behaviour was observed. No notable decrease in haemoglobin or haematocrit was noted in the BI 425809 treatment groups compared with placebo.

For a more detailed list of observed AEs and safety measures please refer to the current Investigator's Brochure, section 6 [[c02155957](#)].

1.2.1.4 Clinical pharmacokinetics

As BI 425809 is a substrate of CYP3A4, co-administration of weak, moderate and strong CYP3A4 inhibitors and inducers is not permitted.

Due to a mild induction potential for CYP3A4 [[c08949593](#)], BI 425809 should be administered with caution in presence of sensitive substrates of these enzymes, and sensitive CYP3A4 substrates with a narrow therapeutic index are not permitted. BI 425809 had no relevant effect on CYP2C9, CYP2C19, and P-gp substrates.

For a more detailed description of the BI 425809 profile please refer to the current Investigator's Brochure [[c02155957](#)].

1.2.2 Donepezil

Donepezil is a specific and reversible inhibitor of acetylcholinesterase, the predominant cholinesterase in the brain. Current theories on the pathogenesis of the cognitive signs and symptoms of Alzheimer's disease attribute some of them to a deficiency of cholinergic neurotransmission [R15-4794]. Donepezil is indicated for the symptomatic treatment of mild to moderate dementia of the Alzheimer's type and commonly used in this patient population [R18-3913].

In mild to moderate AD the dosing recommendation is a daily dose of 5 mg q.d. which might be increased to a maximum dose of 10 mg q.d.. For tolerability reasons, it is recommended to administer donepezil in the evening and to use an up-titration scheme starting with 5 mg donepezil q.d. and increasing to 10 mg q.d. if needed and well tolerated.

Maximum plasma levels after administration of 10 mg donepezil are reached approximately 3 - 4 hours after oral administration [R15-4794, R18-3913].

The terminal disposition half-life is approximately 70 hours. Following multiple dose administration, steady state is reached within ~3 weeks. Donepezil is mainly excreted (57%) in the urine, both intact (17%) and metabolized, and also via faeces (14.5%). It is extensively metabolized to four major metabolites, of which one, 6-O-Desmethyl-Donepezil has a comparable activity to donepezil, and a number of minor metabolites, of which not all have been identified [R18-3913].

In vitro studies have shown that CYP3A4 and to a minor extent CYP2D6 are involved in the metabolism of donepezil. In a study in healthy volunteers, ketoconazole increased mean donepezil concentrations by about 30 %. In patients with mild – moderate hepatic impairment steady state exposures of donepezil were increased (AUC up to ~ 48%, C_{max} up to ~39%) [R18-3913].

Enzyme inducers such as rifampicin, phenytoin, carbamazepine and alcohol may reduce the levels of donepezil [R15-4794].

In human liver microsomes CYP-450 enzymes 1A2, 2C9, 2C19, 2D6 and 3A4 were inhibited by donepezil with IC_{50} values > 100 μ m. In addition, the mean k_i values for CYP-3A4 and CYP-2D6 were calculated to be 131 μ m and 47 μ m, respectively. Clinical studies have shown that the steady-state C_{max} for the 10 mg dose of donepezil is approximately 164 nm. Since it is anticipated that therapeutic concentrations of donepezil are more than 280-fold lower than the lowest k_i value obtained with CYP-2D6 and almost 800-fold lower than the k_i observed with CYP-3A4, it is expected that donepezil will not inhibit the metabolism of other drugs metabolized by these or any other CYP-450 isoenzymes [R18-3919].

Data from clinical trials in healthy volunteers indicate a good safety profile for daily doses up to 10 mg and an acceptable safety profile for a daily dose of 23 mg. This is in accordance with the sponsor's own experience of a trial in healthy volunteers that received multiple doses of donepezil [c09564954]

- A randomized, double-blind, multiple dose study was investigating the pharmacokinetic and pharmacodynamics profile of donepezil, clinical trials with healthy volunteers. Single daily doses of donepezil (5 and 10 mg) each evening were administered on 28 consecutive days.
8 subjects received 5 mg donepezil for 28 days, 8 subjects started with 5 mg donepezil and switched thereafter to a daily dose of 10 mg for the remaining 21 days. Donepezil was well tolerated by all subjects. The most frequently reported adverse events were headache, gastrointestinal upset, sleep disturbance and lethargy. All were transient, mild and resolved during continued treatment without the need for adjunctive therapy [[R05-0853](#)].
- An open-label, randomized, single-dose, two-period crossover study was investigating the bioequivalence of two extended-release tablets of donepezil 23 mg under fasting (n=74) and fed (n= 93) conditions.
In the fasting study, a total of 154 AEs were reported by 52 subjects. Of all AEs, two (increased neutrophil count and oral herpes) were unexpected and possibly related to the administration of the product. In the fed study, 81 subjects experienced a total of 305 AEs. Of all AEs, four (mydriasis, oral herpes, photophobia, and pupils unequal) were unexpected and possibly related to the administration of the (test or reference) products.
No subject was withdrawn from the study for safety reasons. There were no deaths or serious adverse events reported. All of the observed AEs were considered to be resolved. Given this information, the study drugs appeared to be well-tolerated and there were no safety concerns observed [[R15-4356](#)].
- A study to investigate the pharmacokinetic drug-drug interaction following oral administration of BI 409306 and donepezil in 32 healthy male (n = 17) and female (n = 15) subjects. Part 1 of this trial was performed as a one fixed sequence, open-label trial, in which single doses of BI 409306 and multiple doses of donepezil (5 mg qd for 7 days followed by 10 mg qd for 14 days) were administered, Part 2 of this trial was a randomised, open-label, 2-way crossover design, in which single doses of donepezil and multiple doses of BI 409306 were given.
In Part 1 of the trial, i.e. after multiple doses of donepezil, 16 out of 18 subjects (88.9%) were reported with at least 1 AE that was assessed as drug-related. The most frequently reported drug-related AEs were dizziness and nausea (both 55.6% of subjects), followed by headache and fatigue (both 22.2%). Dizziness was only observed after administration of donepezil alone, whereas nausea and headache were observed after administration of donepezil alone and in combination with BI 409306. As expected visual brightness a known AE of BI 409306 was only observed after BI 409306 administration. Fatigue was observed in all 3 treatment phases.
All subjects completed the trial except for 1 subject in Part 1 who withdrew during the second treatment period (donepezil administration) because of AEs that were considered not to be drug-related (lower abdominal pain, haematochezia, and ruptured ovarian cyst) [[c09564954](#)].

According to [[R15-4794](#), [R18-3913](#)], the safety profile mainly results from the cholinergic activity of donepezil, resulting in

- Gastrointestinal symptoms (e.g. nausea, diarrhea, vomiting, abdominal pain, gastric and duodenal ulcers and gastrointestinal hemorrhage)
- Cardiac symptoms (e.g. syncope, bradycardia, sino-atrial block, atrioventricular block)
- Central-nervous symptoms (e.g. syncope, dizziness, insomnia, seizures, extrapyramidal symptoms and neuroleptic malignant syndrome)

Further undesirable effects of donepezil include common cold, anorexia, hallucinations, agitations, aggressive behavior, abnormal dreams and nightmares, liver dysfunction including hepatitis, minor increase in serum concentration of muscle creatine kinase, rhabdomyolysis, rash pruritus, muscle cramps, urinary incontinence, headache, fatigue, pain, and accident.

Donepezil

- Is likely to exaggerate succinylcholine-type muscle relaxation during anesthesia
- Should not be co-administered with other cholinergic agonists or antagonists
- Has minor or moderate influence on the ability to drive and use machines
- May have vagotonic effects on the sinoatrial and atrioventricular nodes manifesting as bradycardia or heart block
- As a cholinomimetic may cause bladder outflow obstruction although this was not observed in clinical trials with marketed Aricept (tradename of donepezil in the US)
- As a cholinomimetic may have the potential to cause seizures
- Should be used with care in patients with history of asthma or COPD as cholinomimetics may cause bronchoconstriction

Neuroleptic Malignant Syndrome (NMS):

NMS, a potentially life-threatening condition characterized by hyperthermia, muscle rigidity, autonomic instability, altered consciousness and elevated serum creatine phosphokinase levels, has been reported to occur very rarely in association with donepezil, particularly in patients also receiving concomitant antipsychotics. Additional signs may include myoglobinuria (rhabdomyolysis) and acute renal failure.

Cholinergic crisis:

Donepezil overdose can result in cholinergic crisis characterized by severe nausea, vomiting, salivation, sweating, bradycardia, hypotension, respiratory depression, collapse and convulsions. Increasing muscle weakness is possible and may result in death if respiratory muscles are involved.

For a more detailed description of the profile of BI 425809, please refer to the current Investigator's Brochure [[c02155957](#)] and for donepezil to the SmPC [[R18-3913](#)].

1.2.3 Residual Effect Period

The Residual Effect Period (REP) of BI 425809 is 11 days, the REP for donepezil 15 days. This is the period after the last dose with measurable drug levels and/or pharmacodynamic effects is still likely to be present.

1.3 RATIONALE FOR PERFORMING THE TRIAL

BI 425809 is being developed for the symptomatic treatment of AD. Donepezil is a specific and reversible inhibitor of acetylcholinesterase and is frequently used for the symptomatic treatment of AD.

Both, BI 425809 as well as donepezil are metabolized via CYP3A4. Clinical data show that BI 425809 is a weak inducer of CYP3A4 and at the same time a sensitive CYP3A4 substrate [c02155957]. As donepezil is a commonly used medication in the target population of BI 425809 the potential and relevance of possible drug-drug interaction shall be investigated with this trial to ensure a safe use in upcoming clinical trials as well as in later clinical use in the target population.

1.4 BENEFIT - RISK ASSESSMENT

Participation in this study is without any (therapeutic) benefit for healthy subjects. Their participation in the study, however, is of major importance to the development of BI 425809. The assessment of the drug-drug-interaction (DDI) potential of BI 425809 and donepezil will contribute to a safe clinical use of this GlyT1-inhibitor in patients with Alzheimer's disease that are also treated with donepezil.

The subjects are exposed to the risks of the study procedures and the risks related to the exposure to the trial medication.

Procedure-related risks

The use of an indwelling venous catheter for the purpose of blood sampling may be accompanied by mild bruising and also, in rare cases, by transient inflammation of the wall of the vein. In addition, in rare cases a nerve might be injured while inserting the venous catheter, potentially resulting in paresthesia, reduced sensibility, and/or pain for an indefinite period. The same risks apply to veinipuncture for blood sampling.

The total volume of blood withdrawn during the entire study per subject will not exceed the volume of a normal blood donation (500 mL). No health-related risk to healthy subjects is expected from this blood withdrawal.

Drug-related risks and safety measures

Risks related to BI 425809 administration

In Part 2 of this trial, a dose of 25 mg BI 425809 q.d. will be administered over a period of 24 days. Multiple oral doses of 25 mg BI 425809 have already been administered in trial

1346.2 [[c02958024](#)] (12 days) and 1346.3 [[c03724403](#)] (14 days) and considered safe and well tolerated (for details please refer to [Section 1.2.1.3](#)). Further, two Phase II trials, one in patients with Alzheimer's disease (1346.23) and one in patients with CIAS (1346.9), are currently ongoing in which patients receive up to 25 mg BI 425809 q.d. in an ambulatory setting over a period of 12 weeks with no safety issues reported so far.

Based on its mechanism of action, its preclinical profile and the data obtained from ongoing and completed Phase I/II studies so far, there is no indication that BI 425809 should be regarded as a high risk compound.

The main dose-limiting AEs observed so far, were expected based on its mode of action. These adverse CNS symptoms, including dizziness, headache, and visual effects showed a trend towards dose dependency and were monitorable and reversible after treatment discontinuation. The reported adverse events were mostly of mild to moderate intensity and did not jeopardize the subject's wellbeing. Adequate safety monitoring including neurological examinations, vital signs/ECG, visual tests, safety laboratory, suicidality assessment and adverse events monitoring has been implemented. Though the trial is designed in parts in an ambulatory fashion, if the investigator has any clinical concern the safety of the subject will be paramount and the inpatient stay will be extended or initiated.

Risks related to donepezil administration

Multiple doses of donepezil up to 10 mg were well tolerated in healthy volunteer trials [[R15-4355](#), [R05-0853](#), [c09564954](#)]. With single doses up to 23 mg donepezil, the safety profile was still summarized as "well tolerated" and did not raise safety concerns [[R15-4356](#)]. The safety profile of donepezil is mainly driven by cholinergic effects that in case of overdose may lead to a cholinergic crisis (see [Section 1.2.2](#)). Symptoms resulting from the cholinergic effects of donepezil are monitorable and can be adequately treated (see [Section 4.2.1](#)).

Risks related to the combined administration of BI 425809 and donepezil

BI 425809 and M530 were determined to be mild in vitro irreversible inhibitors of CYP3A₄; however, once daily oral administration of BI 425809 (25mg) did not inhibit CYP3A₄-mediated elimination of midazolam in humans (1346.22 [[c08949593](#)]). Mild in vitro reversible inhibition of CYP2D6 (IC₅₀ >100 µM) by M530 is not expected to be of clinical impact based on exposures associated with 25 mg qd (C_{max} 25 mg 278 nmol/L, AUC_{0-inf} 12700nmol*h/L [[c02155957](#)]) and the minor contribution of CYP2D6 to donepezil metabolism compared to CYP3A₄. Therefore an increase of donepezil exposure after BI 425809 administration is not to be expected.

On the opposite, as BI 425809 has been shown clinically to be a weak inducer of CYP3A₄ and may therefore reduce levels of donepezil as it has been shown for other enzyme inducers such as rifampicin, phenytoin, carbamazepine and alcohol [[R15-4794](#)].

Regarding donepezil, no inhibition of the metabolism of drugs metabolized by CYP-450 isoenzymes is expected at therapeutic doses of donepezil ([Section 1.2.2](#)).

In summary, a clinically relevant pharmacokinetic interaction causing elevated exposures of donepezil or BI 425809 is considered unlikely.

Safety measures

- Close monitoring of
 - Adverse events
 - Safety lab (special focus on hepatic parameters, markers of GI bleeding (CRP, haematology, iFOB), CK)
 - ECG (focus on possible vagotonic action of donepezil)
 - Vital signs
- Prohibition to use drugs as concomitant therapy that are known to also trigger gastrointestinal ulcers/hemorrhage, e.g. NSAIDs ([Section 4.2.2](#))
- Availability of rescue medication (atropine) in case of signs and symptoms of cholinergic crisis (see [Section 4.2.1](#)).
- Subjects will receive a trial specific emergency card with information for anesthesiologists about the donepezil intake in case of unplanned surgery and potential use of succinylcholine
- As donepezil may impact the ability to operate vehicles and/or machines, subjects participating in Part 1 of this trial subjects are not allowed to drive a vehicle or operate machines during Visit 3
- Although only healthy subjects are allowed to enter this trial per se the investigator has to specifically ask subject's for any life-time history of asthma or seizure resulting in exclusion of the subject

Although rare, a potential for drug-induced liver injury is under constant surveillance by sponsors and regulators. Therefore, this study requires timely detection, evaluation, and follow-up of alterations in selected liver laboratory parameters to ensure subjects' safety.

Overall assessment

Considering the good safety profile of BI 425809 observed so far in healthy subjects, and the safety and tolerability of donepezil up to single doses of 23 mg in healthy volunteers, the unlikelihood of increased drug exposures due to a donepezil-BI 425809 interaction and taking into account the safety measures described in this chapter, the benefit of a successful clinical development of BI 425809 for the treatment of Alzheimer's disease or CIAS is assessed to outweigh the potential risks to healthy subjects participating in this trial that are further considered to be low and acceptable.

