	26	600:00	18:00	Ambulatory visit ¹¹ , admin. 10 mg donepezil		x ⁸					x ^{2,7}	
	27	624:00	18:00	Ambulatory visit ¹¹ , admin. 10 mg donepezil		x ⁸					x ^{2,7}	
	28	648:00	18:00	Ambulatory visit ¹¹ , admin. 10 mg donepezil		x ⁸					x ^{2,7}	
29	672:00	18:00	Ambulatory visit ¹¹	x ¹⁰	x ⁸			x ²	x ²	x ^{2,7}		
4	44-49	n.a.	n.a.	End of trial examination ⁴	x ¹⁰			x ^{12,13}	x	x	x	

1. Screening includes subject information, informed consent, physical examination including neurological assessment, check of vital signs, visual tests, ECG, safety laboratory (including drug screening, alcohol breath test, urine pregnancy testing in females, and faecal occult blood test), demographics (including determination of body height and weight, smoking status and alcohol history), relevant medical history, concomitant therapy and review of inclusion/exclusion criteria.
2. The time is approximate; the procedure is to be performed and completed within 2 h prior to drug administration.
3. If several actions are indicated at the same time point, the intake of meals will be the last action.
4. End of trial examination includes physical examination including neurological assessment, vital signs, visual tests, ECG, safety laboratory, urine pregnancy testing in females, recording of AEs and concomitant therapies, faecal occult blood test.
5. Including urine drug screening and alcohol breath test and urine pregnancy testing in females
6. AEs and concomitant therapies will be recorded throughout the trial, but will be specifically asked for at the time points indicated in the [Flow Chart](#) above.
7. Includes questioning for 'restrictions'

8. Pre-dose PK, i.e. within 10 min prior to the next drug administration
9. Safety laboratory to be taken within 3 days prior to first trial drug administration of Visit 2 and 3. All results must be available and be checked by the investigator or his/her designee before trial drug administration. For Visit 3, the safety laboratory of day 8, Visit 2 will be used.
10. Includes immunochemical faecal occult blood (iFOB) test
11. Discharge after confirmation of fitness by the investigator/designee
12. Neurological assessment (i.e. Romberg and Unterberger test, assessment of gait, further tests as needed) to be performed at the time points mentioned in the [Flow Chart](#) above and at any times CNS adverse events are reported

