4.1.1 Identity of the Investigational Medicinal Products

The characteristics of the trial products are given below:

Trial product 1:

Substance:	BI 425809
Pharmaceutical formulation:	Film coated tablet
Source:	BI Pharma GmbH & Co. KG, Germany
Unit strength:	25 mg
Posology:	Part 1: 0-0-1 Part 2: 1-0-0
Route of administration:	Oral
Duration of use:	Part 1: single dose on Day 1, Visit 2, and on Day 22, Visit 3 Part 2: multiple doses on days 1-24, Visit 3

Trial product 2:

Name:	Donepezil-HCl-ratiopharm®
Substance:	Donepezil
Pharmaceutical formulation:	Film-coated tablet
Source:	Ratiopharm GmbH, Germany
Unit strength:	5 mg
Posology:	Part 1: 0-0-1 (Days 1-7, Visit 3) and 0-0-2 (Days 8-28, Visit 3) Part 2: 2-0-0
Route of administration:	Oral
Duration of use:	Part 1: multiple doses on days 1-28, Visit 3 Part 2: single dose on Day 1, Visit 2 and on Day 10, Visit 3

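### The Part 1 driving ban is imposed because of donepezil but ends with Visit 3, 24 h after the last 10 mg dose, when donepezil is still at about its steady-state trough

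*Protocol*

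**What the plan says.** Among the safety measures in Protocol 1.4, the possible effect of donepezil on operating vehicles or machines is the reason for this rule: "subjects participating in Part 1 of this trial subjects are not allowed to drive a vehicle or operate machines during Visit 3". Protocol 1.2.2 describes the effect itself: "Has minor or moderate influence on the ability to drive and use machines".

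Donepezil dosing is set out in 4.1.1: "Part 1: multiple doses on days 1-28, Visit 3". In the Part 1 Flow Chart the last 10 mg dose is on Day 28 (648:00), and the last Visit 3 row is the ambulatory visit on Day 29 (672:00). The next scheduled contact is the end of trial examination on Day 44-49.

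Protocol 1.2.3 gives the residual effect periods: "The Residual Effect Period (REP) of BI 425809 is 11 days, the REP for donepezil 15 days". It defines the term: "This is the period after the last dose with measurable drug levels and/or pharmacodynamic effects is still likely to be present".

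The diet and life-style restrictions in 4.2.2.2 contain no driving rule. No other visible section extends the ban beyond Visit 3.

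**The concern.** The ban exists because of the drug, but it stops at a visit label. With a half-life of nearly three days and 21 consecutive 10 mg doses, exposure one day after the last dose is almost what it was through the last week of dosing, when driving was forbidden. A subject who follows the rule as written may drive from Day 30, and from the evening of Day 29 if the ban is read as ending with that visit. No scheduled visit follows for about two weeks.

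What is at stake is the safety of healthy volunteers, who gain no therapeutic benefit, and of other road users. In the sponsor's earlier interaction study of donepezil with another compound (Protocol 1.2.2), dizziness was one of the two most frequent drug-related adverse events, in 55.6% of 18 subjects (10 subjects), and was seen on donepezil alone. No PK endpoint of this trial is affected.

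**Working it through.** **Inputs**
- Half-life (Protocol 1.2.2): "The terminal disposition half-life is approximately 70 hours". The 60-80 h range below is my assumption.
- Doses (Protocol 4.1.4, Table 1): 7 x 5 mg, then 21 x 10 mg, every 24 h from 0 h; last dose at 648 h.
- Visit 3 ends at 672 h (Part 1 Flow Chart).
- Donepezil REP: 15 days = 360 h (Protocol 1.2.3).

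**The plan's own figures first.** 7 x 5 + 21 x 10 = 245 mg, as in Table 4.1.4: 1. The REP is 360/70 = 5.1 half-lives. Twenty-one days of dosing reach 1 - 2^(-504/70) = 99.3% of steady state, in line with the protocol's statement of about three weeks.

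**Level when the ban ends.** I assume first-order elimination with superposition and express amounts as mg-equivalents remaining.
- k = ln 2/70 = 0.00990 per h; r = exp(-24k) = 0.7885.
- Steady-state 10 mg trough = 10r/(1 - r) = 37.28 mg.
- Amount at 672 h, summed over 28 doses = 37.13 mg.
- Ratio = 1 - 0.5r^21 - 0.5r^28 = 99.6%.

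**Decline afterwards**, as a percentage of the steady-state trough, from the 672 h value times 2^(-t/half-life):

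| Time | 60 h | 70 h | 80 h |
|---|---|---|---|
| Day 29, 18:00 (672 h) | 99.8 | 99.6 | 99.2 |
| Day 30, 08:00 (686 h) | 85 | 87 | 88 |
| 2 days after Day 29 (720 h) | 57 | 62 | 65 |
| 7 days after Day 29 (840 h) | 14 | 19 | 23 |
| End of REP (1008 h) | 2.1 | 3.6 | 5.4 |

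**Time left uncovered.** The REP ends at 648 + 360 = 1008 h (Day 43, 18:00). 1008 - 672 = 336 h, which is 14 of its 15 days. The SAP treats all of this time as on-treatment (Table 6.1: 3). The combined phase runs to 504 + 264 = 768 h (Day 33), which is 4 days past 672 h. The donepezil phase covers the other 10 days.

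**A reference for a shorter period.** Part 2 subjects may go home 72 h after a single 10 mg dose, and no driving ban is stated for them. The amount then is 10 exp(-72k) = 4.90 mg. The Day 29 amount is 37.13/4.90 = 7.6 times that. It falls to that level in ln(7.57)/k = 204.5 h = 8.5 days, which is 9.5 days after the last dose (8.1 days at 60 h, 11.0 days at 80 h).

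**The case against.** The strongest reply is that level is not effect. Up-titration is used for tolerability, and in the cited 28-day evening-dosing study the adverse events were mild, transient and resolved while dosing continued. The same concentration after four weeks need not impair as it might on Day 1. The 55.6% dizziness figure belongs to the dosing period of another study. The documents give no course after the last dose, and the influence on driving is called minor or moderate. All of this stands, so the size of any impairment is unknown. It does not explain the end date, because adaptation of that kind would apply equally to the last week of dosing, when the ban is kept.

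The REP is used for exposure and for assigning adverse events. It is not a driving standard. That also stands, and it is why a shorter justified period is acceptable.

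Safeguards exist. The Day 29 visit carries this footnote: "Discharge after confirmation of fitness by the investigator/designee". It also has ECG, vital signs, safety laboratory and adverse event questioning. CNS events trigger a neurological assessment (headache excepted, unless the investigator wants one), and an inpatient stay can be started on clinical concern. These reduce the risk but tell the subject nothing about driving afterwards. The consent pages were removed, so longer advice there cannot be ruled out.

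Three stronger readings are tempting, and the documents support none of them:
- **Subjects are released with donepezil at or above every trough under the ban.** This is true only at 672 h. By midnight (678 h) the amount is 34.98 mg (94% of the steady-state trough), below 11 of the 27 earlier daily troughs. By 08:00 on Day 30 it is below 14 of them. A trough is also the low point of the dosing interval: with an assumed tmax of 3.5 h, the Day 29 level is about 81% of the steady-state peak.
- **The trough after the first 5 mg dose is a level the sponsor judged unsafe for driving.** The ban simply starts when dosing starts. Part 2 subjects leave with about 4.9 mg-equivalents and no stated ban, more than the 3.94 mg of that first trough.
- **Subjects are shown to be unfit to drive up to Day 43.** Nothing in the documents measures impairment after the last dose.

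**Conclusion.** The point holds as a mismatch between a safety rule and its own reason. The ban is justified by donepezil but ends when donepezil is at about 99.6% of its steady-state trough (99.2-99.8%), with 14 of 15 REP days left and no visit until Day 44-49. It should be corrected because the change is cheap and concerns subject safety. It does not show that subjects would be impaired, and it has no bearing on the PK results.

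The conclusion rests on linear first-order kinetics with a half-life near 70 h; on Day 29 being the end of Visit 3, which is read from the Flow Chart because the text gives no separate end date; and on no longer driving instruction in the removed subject information.

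**What to change.** In Protocol 1.4, for Part 1, replace the Visit 3 limit with a period from the first donepezil dose to a stated time after the last donepezil dose actually taken. The default is 15 days, the donepezil REP. With full dosing that is Day 43, before the end of trial examination. A shorter period is acceptable if the text justifies it: about 10 days brings donepezil to roughly the level at which Part 2 subjects are discharged. Counting from the last dose taken also gives early discontinuers a clear end date. List the rule in 4.2.2.2, where the exercise restriction already runs to the end of trial examination, and match the subject information.

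Subjects bear the cost: up to 14 more days without driving for 18 subjects, at most 18 x 14 = 252 subject-days, with possible travel arrangements. No visit, procedure or sample is added, and the PK analysis is unchanged.
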